4.2.3.1 NK cells and tumor spreading

Under physiologic circumstances, tumor cells are believed to be caught and destroyed through cell-mediated immune responses involving NK cells.^{74,75} As mentioned previously, these complex immune interactions are usually impaired during the perioperative period: surgical stress, for instance, has been suggested to induce a generalized inflammatory state that is thought to suppress NK cells activity and therefore enhance tumor spreading.^{76,77} Further weakening of the immune response is believed to occur through drug-related effects of anesthetics on NK cells (table 3). The vast majority of these studies were either not controlled or not appropriately controlled, yielding results that are difficult to compare.

Table 3. Summary of search results: NK cells studies

Study ID	Design	Comparison (not considered)	Population (nb analysed)	Endpoint(s)	Results
VOLATILE ANESTHETICS VERSUS PROPOFOL					
Zhang 2014	RCT	1. Propofol 2. Propofol + Sevoflurane 3. Sevoflurane	Reconstructive surgery for tongue carcinoma (60)	NK cells, T-lymphocytes, B-lymphocytes levels	Significant decrease in all cells levels after exposure to anesthetics in all groups. No difference between groups.
Zanda 1991	Prospective, controlled	1. Propofol 2. Isoflurane	Abdominal surgery	Nk cells cytotoxic activity	No difference between groups
PROPOFOL					
Brand 2003	Prospective, not controlled	All patients received propofol anesthesia.	Elective orthopedic surgery (30)	NK cells, T-lymphocytes, B-lymphocytes levels	Significant decrease in NK cells levels after exposure to anesthetics.
VOLATILE ANESTHETICS					
Brand 1997	Prospective, not controlled	All patients received isoflurane anesthesia.	Elective orthopedic surgery (30)	NK cells, T-lymphocytes, B-lymphocytes levels	Significant decrease in NK cells levels after exposure to anesthetics.
Kutza 1997	Prospective, not controlled	All patients received isoflurane anesthesia.	Various surgical settings (26)	NK cells (number and cytotoxic activity)	Significant decrease in the cytotoxic activity of NK cells; significant decrease in the relative number of NK cells (% of total white blood cells) but not in absolute numbers.
Markovic 1993	Prospective, controlled, in vivo (mice)	1. Halothane 1.5% (2hrs) 2. Isoflurane 2.1% (2hrs)	Mice (nb not reported)	Nk cells cytotoxic activity	No difference in baseline cytotoxic activity; significant reduction in IFN-induced cytotoxic activity in both exposure groups.
OTHER COMPARISONS					
Miyata 2013	Prospective, controlled, in vivo (dogs)	1. Propofol induction + isoflurane (3hrs) 2. No anesthesia	Dogs (13)	NK cells cytotoxic activity	In dogs exposed to anesthetics, significant decrease in NK cells cytotoxic activity
Richardson 1997	Prospective, not controlled	Most patients received propofol + isoflurane anesthesia	Uveal malignant melanoma (19)	NK cells cytotoxic activity	Increase in perioperative NK cells cytotoxic activity
Pirttikangas 1994	RCT	1. Propofol 2. Thiopental + Nitrous oxide 70%	Biopsy for breast cancer (27)	NK cells, T-lymphocytes, B-lymphocytes levels	Significant decrease in NK cells levels in both groups. No difference between groups.
Bentley 2005	RCT	1. Propofol + Ketamine + isoflurane 2. Propofol + isoflurane	Maxillofacial surgery (59)	NK cells (number and cytotoxic activity)	Significant decrease in cytotoxic activity in both groups, no difference between groups. No difference in the % of NK cells.

Studies related to breast cancer research are highlighted in bold. YELLOW = mixed results or no difference or not adequately controlled

[figure not shown]
4.2.3.2 CTC and extracapsular spread in lymph nodes

While lymph node status has been regarded as the most important prognostic factor for disease-free and overall survival in breast cancer patients,⁷⁸ a substantial amount of node-positive patients will surprisingly remain free of systemic relapse.⁹ By contrast, some patients expected to have a favorable outcome will experience the opposite scenario, suggesting that other factors play a role in the metastatic cascade.

Recent findings suggests that extracapsular spread (ECS) of tumor cells observed in axillary lymph node contents might correlate with poorer prognosis in breast cancer patients.⁷⁹ According to the yearly statistics of our hospital, axillary node dissection is realized in more than 30% of women undergoing surgery for primary breast cancer. The correlation between CTC positivity and the presence of ECS in the histopathological findings of axillary lymph node contents will be assessed in these patients.

[figure not shown]
4.3 Investigational Product and Dose Rationale

Sevoflurane is a halogenated general inhalation anesthetic drug. It is chemically stable and is neither flammable nor explosive in clinical concentrations. It belongs to the group of halogenated ethers, and its structural formula is:

Sevoflurane is an inhalational anesthetic agent for induction and maintenance of general anesthesia. The minimum alveolar concentration (MAC) of sevoflurane in oxygen for a 40-year-old adult is 2.1%. Because of its little solubility in blood and tissues its effects are of rapid onset. Recovery of consciousness is usually achieved within 8 to 10 minutes after discontinuation of application. The use of sevoflurane as a general anesthetic is well established, and considered as a safe, routinely prescribed, anesthetic agent.

Propofol is an intravenous hypnotic agent, poorly soluble in water, thus dissolved in a fat emulsion vehicle that contains soya bean oil, triglycerides, egg lecithin, glycerol, sodium oleate and water.

Its hypnotic effect occurs rapidly (less than 60 seconds), but the effect duration is short, due to rapid redistribution and metabolism. It is a well-established drug, which has been successfully used for general anesthesia or sedation since more than 20 years.

Since the emergence of short acting intravenous anesthetics in the late 80's, an impressive amount of literature comparing volatile with intravenous anesthesia has been produced, focusing on pharmacological effects, patient safety, quality process, patient satisfaction, or organ protection. No consensus regarding the superiority of one technique has been reached so far, mainly because complications related to anesthesia are more the result of multiple factors (surgery, patient specific health problems) rather than due the drug itself. Both sevoflurane and propofol contribute equally to the following systemic effects observed during general anesthesia:

- Cardiovascular: hypotension (fall in systemic resistance), bradycardia.
- Respiratory: reduced minute ventilation, reduced respiratory threshold to hypoxia, increased tolerance to hypercapnia.
- Central nervous system: autoregulation maintained, decrease in cerebral blood flow and oxygen consumption.

If both drugs produce similar physiologic effects, they differ however regarding specific side effects:

- in susceptible patients, Sevoflurane can trigger malignant hyperthermia, a hypermetabolic state due to abnormal calcium release in skeletal muscle (pharmacogenetic disease, autosomal dominant).
- Sevoflurane and other volatile anesthetics are suggested to confer organ protection, a property known as "volatile preconditioning"
- Propofol is known to decrease the incidence of postoperative nausea and vomiting in susceptible individuals
- In soya- or egg-allergic patients, the administration of propofol can induce anaphylactic reactions

The choice between the different regimens of anesthesia maintenance (volatile vs. intravenous) is mostly dictated by habits and local hospital practices.

4.4 Risk/Benefits and Ethical Considerations

By means of this trial, we might be able to identify potential targets playing a crucial role in the metastatic cascade. Being able to find the best (or the least harmful) anesthesia regimen for cancer patients is of primary relevance, and raises important ethical concerns in terms of beneficence and non-maleficence.

5. STUDY OBJECTIVES AND OUTCOMES

We will conduct a prospective, randomized, double blinded, controlled study over a 52-month period to investigate whether commonly used anesthetics (volatile *versus* intravenous) affect the level of circulating tumor cells in patients undergoing surgery for primary breast cancer.

Hence, the **primary objective** is to compare the effects of 2 anesthetic regimens (sevoflurane *versus* propofol) on perioperative CTC levels measured at 4 different time points. Blood levels (i.e. number) of CTC will be determined using the CellSearch® approach, as described below.

Two **secondary objectives** will be determined:

A) To determine if anesthesia interferes with NK cells by measuring NK cells number and activity at 4 different time points;

B) To establish if the level of CTC correlates with the presence of ECS in the histopathological findings of axillary lymph nodes (exclusively in patients undergoing breast surgery with axillary dissection).

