Objective(s)/ Outcome(s):	> Primary outcome: to determine if there is a difference in the mean of blood CTC levels over time among patients exposed to volatile anesthetics (i.e. receiving sevoflurane) compared to patients in the control group (i.e. receiving intravenous anesthesia with propofol) > Secondary outcomes: A) to determine if anesthesia interferes with the number and activity of blood natural killer (NK) cells

	B) to examine if CTC levels correlates with the presence of extracapsular spread of tumor cells (ECS) in the histopathological findings in axillary lymph nodes
Number of Subjects:	Total number of 232 patients.
Diagnosis and Main Inclusion Criteria:	
Diagnosis: primary breast cancer
 
Inclusion Criteria:
 
 > Female > Age 18 to 85 > ASA I-III > Primary breast cancer (TNM stage = T1-3, N0-2, M0) > Primary surgery > Written informed consent
Main Exclusion Criteria:	
 > Metastatic breast cancer > Other than primary surgery (recurrence, reconstruction) > Pre-operative chemotherapy or radiotherapy > Auto-immune disease, HIV, other active cancer, age>85, ASA IV or V > Concomitant regional anesthesia > Chronic opioids medication > Any systemic immunosuppressive therapy > Known hypersensitivity or suspected allergy to propofol, soya or egg proteins > Known hypersensitivity to volatile anesthetics (malignant hyperthermia) > Pregnancy > Breast feeding > Non German-speaking patients > Enrollment in any other clinical trial during the course of this trial, 30 days prior to its beginning or 30 days after its completion
Study Product, Dose, Route, Regimen:	Sevoflurane will be used in its inhalational form via an endotracheal tube for maintenance of anesthesia. The dose and regimen will be adjusted to keep an adequate depth of anesthesia (MAC 0.8-1.2), according to BIS values between 40 and 60
Duration of administration:	Administration will be limited to the length of the surgical procedure
Reference therapy, Dose, Route, Regimen:	Propofol will be intravenously administered via a target-controlled infusion (TCI) device providing a drug dose ranging from 3.0 to 5.0 mcg/ml. The dose and regimen will be adjusted to keep an adequate depth of anesthesia, attested by BIS values between 40 and 60.
Study Schedule:	March 2014 to July 2018

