6. STUDY DESIGN

6.1 General Design

We will conduct a prospective, randomized, double blinded, controlled study over a period of 52 months. We will consider adult female patients undergoing surgery for primary breast cancer. Expecting a dropout rate of 10% over time, we will recruit a total of 232 patients (i.e. 116 in each study group).

Patients will be screened for eligibility according to the inclusion and exclusion criteria on the day prior to surgery. Written informed consent will be subsequently obtained. A pregnancy test will be performed for all included patients.

On the day of operation, the patients will be premedicated with midazolam *per os* (3.75mg to 7.5mg). Randomization will be performed according to a computer-generated anesthesia-assignment (www.randomizer.at) once the patient will be installed for induction of anesthesia. By this means, concealment of random allocation will be ensured.

After preoxygenation, induction of anesthesia will be administrated in both groups similarly, using fentanyl 2-3mcg/kg, Pentothal 4-6 mg/kg and rocuronium 0.6mg/kg intravenously. Maintenance of anesthesia will be conducted following the assignment group:

1) in “Group Sevo”, anesthesia will be maintained with sevoflurane in 80% oxygen, adjusted to keep an adequate depth of anesthesia (minimal alveolar concentration (MAC) between 0.8 and 1.2), attested by bispectral (BIS) index values between 40 and 60.

2) in “Group Propofol” anesthesia will be maintained with a target-controlled infusion (TCI) device providing an intravenous propofol dose adjusted to keep an adequate depth of anesthesia (TCI values: start after induction with 2.0mcg/ml, then ranging from 3.0mcg/ml to 5.0mcg/ml), attested by BIS index values between 40 and 60.

Patients will be ventilated with 80% oxygen in air.

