6.3 Secondary Endpoints

6.3.1 Anesthesia, NK cells and tumor spreading

The assessment of NK cells (mean number and activity) will be performed at 4 pre-definite time points, concomitant to CTC determination. The analysis will account for the effect of repeated measurements over time (within-subject factor) and the effect of anesthesia regimen (between-subject factor) as described under section 12.

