9.2 Study drug administration

Sevoflurane or propofol will be administrated according to patient allocation. Because patients scheduled for breast cancer surgery will need a general anesthesia in any case, regardless of their participation to this study, both drugs will be provided by the UHZ.

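### Secondary objective A asks about anesthesia as such, but the trial can only compare sevoflurane with propofol on NK cells; the objective should be worded to match that contrast

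*Protocol*

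**What the plan says.** The synopsis gives secondary outcome A as "to determine if anesthesia interferes with the number and activity of blood natural killer (NK) cells". Section 5 repeats the question and adds the means of answering it: "To determine if anesthesia interferes with NK cells by measuring NK cells number and activity at 4 different time points". Neither sentence says what anesthesia is compared with.

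The primary objective, in the same section, does name its comparison: "to compare the effects of 2 anesthetic regimens (sevoflurane *versus* propofol) on perioperative CTC levels measured at 4 different time points".

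Section 6.3.1 describes the NK analysis: "The analysis will account for the effect of repeated measurements over time (within-subject factor) and the effect of anesthesia regimen". The sentence goes on to label regimen the between-subject factor and refers to section 12 for the description. Section 12 sets out its mixed models for CTC and does not mention NK cells, although section 12.3 places all secondary analyses under intention-to-treat.

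On exposure, section 9.2 states: "Because patients scheduled for breast cancer surgery will need a general anesthesia in any case, regardless of their participation to this study". Section 6.1 states that "induction of anesthesia will be administrated in both groups similarly"; the arms then differ in maintenance only.

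**The concern.** Taken literally, objective A is a question about anesthesia against no anesthesia, answered by serial measurement. No arm goes without anesthesia or without surgery, so the design cannot answer it.

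The change from visit 2 to later visits is not randomised and has several possible causes that the protocol itself names. Section 4.2.3.1 lists surgical stress as a suspected cause of NK suppression, and sections 5.2.3 and 8.3.2.1 say opioids may inhibit immune function. The same section 4.2.3.1 criticises most earlier NK studies for lacking adequate control.

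At stake is how a named secondary objective is reported. A fall in NK cells in both arms could be read as answering the objective as written, although it would not isolate an effect of anesthesia.

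**Working it through.** **The plan's own figure.** There is no sample size for NK cells. The only one, 116 per group in section 12.5, was set for CTC. It reproduces closely with effect size 0.3, within-subject correlation 0.4, two-sided 5%, 80% power and 10% dropout, if three visits are averaged under equal correlation (my assumption):

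- Single measurement: n = 2 × (1.960 + 0.842)² / 0.3² = 174.4 per group.
- Three visits: factor (1 + 2 × 0.4)/3 = 0.60, so 174.4 × 0.60 = 104.7; divided by 0.9 this is 116.3.
- Four visits: factor (1 + 3 × 0.4)/4 = 0.55, so 95.9; divided by 0.9 this is 106.6, which does not match.

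The point about objective A does not depend on this figure, and rewording does not change it.

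**What each contrast contains.**

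| Contrast | What it contains | Randomised? |
|---|---|---|
| Change over time within an arm | Induction, maintenance drug, surgery, opioids, passage of time | No |
| Sevoflurane minus propofol after induction | Difference between maintenance drugs, including its consequences | Yes |
| Anesthesia minus no anesthesia | The literal objective A | No such arm |

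Induction is common to both arms, so it does not confound the second row. It is part of the reason why the first row cannot be attributed to a study drug.

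**Whether the first two rows can come apart.** Table 3 of the protocol has one trial with this study's own contrast, in tongue carcinoma surgery: "Significant decrease in all cells levels after exposure to anesthetics in all groups. No difference between groups". If that pattern recurred here, there would be a change over time and no regimen effect. The breast biopsy trial shows a similar pattern, "Significant decrease in NK cells levels in both groups. No difference between groups", but it compared propofol with thiopental plus nitrous oxide. The maxillofacial trial tested the addition of ketamine. It found lower cytotoxic activity in both groups without a group difference, and no difference in the percentage of NK cells. Neither of these two compares sevoflurane with propofol.

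**Why the visits should be stated.** Section 6.3.1 names time and regimen over four visits. By section 6.4.2, the visit 2 sample is taken before induction, so the expected regimen difference there is zero. Suppose the difference is a constant δ at visits 3, 4 and 5, and the answer is taken from a regimen main effect that weights four complete visits equally:

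(0 + δ + δ + δ)/4 = 0.75 δ.

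A contrast over visits 3 to 5 gives (δ + δ + δ)/3 = δ. The protocol does not say which of these will be used.

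**The case against.** The strongest reply is that the protocol already has the right comparison. Section 6.3.1 makes regimen the between-subject factor for the NK endpoint, and regimen in this trial means sevoflurane or propofol. The stated aim in section 4.1 is comparative, and section 12.3 puts all secondary analyses under intention-to-treat with a per-protocol comparison, which makes sense only for randomised arms. In that setting, objective A can be read as shorthand for the anesthetic regimen. This stands, and it is why the defect is small.

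Three stronger readings are tempting, and the protocol does not support them:

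- A reader might infer that the trial plans to report before-after change as an effect of anesthesia. No section says so, and section 4.2.3.1 shows that the authors know surgery is a competing cause.
- A reader might infer that a fall over time with no difference between arms gives opposite answers to one question. These are compatible results for two different questions.
- A reader might infer that the NK analysis is missing because section 12 is silent on NK cells. The model detail for a secondary endpoint may lie in a statistical analysis plan that is not shown, so that silence is not a fault in itself.

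The reply does not remove the wording. The objective in both places lacks a comparator, while the primary objective beside it has one.

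**Conclusion.** The concern holds as a minor defect of wording. Objective A, in the synopsis and in section 5, asks a question that a trial without an unanesthetised or unoperated arm cannot answer. The answerable question is the sevoflurane-propofol difference that section 6.3.1 already implies.

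The structural point rests on no numerical assumption. The 0.75 factor is conditional: it assumes a constant difference after induction, equal weight on four complete visits, and use of the regimen main effect. A regimen-by-time model that excludes a difference at visit 2 would avoid it. The factor is a reason to state the contrast and does not show that the planned analysis is diluted.

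**What to change.** - **Synopsis and section 5:** reword objective A as a comparison of NK number and NK activity between sevoflurane and propofol.
- **Section 6.3.1:** state that the randomised regimen contrast over visits 3 to 5, adjusted for the visit 2 value, answers objective A. A regimen-by-time mixed model with the visit 2 means constrained to be equal between arms is an equivalent choice.
- **Section 6.3.1:** add that change over time within arms is descriptive and will not be attributed to anesthesia.

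The cost is a few sentences and a narrower claim than the present wording suggests. The visit 2 sample is already collected, so no new data are needed, and the CTC-based sample size is unaffected.

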5.1 Primary Variable: circulating tumor cells (CTC)

Blood CTC levels (i.e. number of CTC per 7.5ml of blood) will be measured before and after the administration of anesthetics using the CellSearch® system, as described elsewhere:^{9,80,81} 15ml sample of peripheral blood (necessary amount for 2 CellSearch® tubes) will be collected at 4 pre-defined time points and screened for CTC within 96 hours of blood collection.

5.2 Secondary Variables

5.2.1 Secondary variable A: NK cells (number and activity)

Assessment of NK cells will be performed at 4 pre-definite time points, concomitant to CTC determination, using 2x8ml of peripheral venous blood collected in sterile tubes containing sodium heparin. The number of NK cells will be assessed using flow cytometry, whilst the NK cells activity will be determined *in vitro* by a direct, cell-based cytotoxicity assay against the K562 (human chronic myelogenous leukaemia) cell line with a fluorescent read-out, as previously described.^{82,83}

5.2.2 Secondary variable B: extracapsular tumor spread (ECS)

After study completion, pathology reports from patients undergoing surgery with axillary lymph node dissection will be reviewed for extracapsular tumor spread with the aim to establish if blood CTC levels correlates with the presence of ECS.

5.2.3 Other study variables

Demographics and perioperative data will be collected as presented in table 4. Since opioids have been suggested to inhibit the immune function,⁸⁴ perioperative analgesia will be administered following a standardized protocol and will be documented thoroughly. Restriction and stratified randomization are expected to minimize the risk of unbalanced confounders (section 12). However, since we will perform exploratory analyses whenever there is a need to control for residual confounders, the following variables will be collected: hypothermia, blood transfusion, administration of cyclooxygenase inhibitors, beta-blockers, glucocorticoids and date of last menstruation.⁸⁵⁻⁸⁷

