
Statistical Methodology:
	
Primary analysis : the number of CTC in peripheral blood will be measured before and after exposition to general anesthesia using a linear mixed model with random effects matrix, which accounts for within-subject treatment factor (i.e. anesthesia regimen)
 
Secondary analyses: since most reports refer to CTC levels as a binary outcome (i.e. positive versus negative endpoints using a cut-off value of $\geq 5\text{CTC}/7.5\text{ ml blood}$), data transformation from continuous into a binary variable will be performed using the same cut-off value. This new data set will be analyzed using a logistic regression mixed model with random effects matrix.
 
All primary and secondary analyses will be performed following an intention-to-treat (IIT) model. This analysis will subsequently compared to a per-protocol analysis to ensure stability of results. Results will be reported as OR, 95% confidence intervals and their associated p-values. A p-value < 0.05 will be considered statistically significant

GCP Statement:
	
This study will be conducted in compliance with the protocol, the current version of the Declaration of Helsinki, and ICH-GCP as well as all national legal and regulatory requirements.

STUDY SCHEDULE

Study Periods	Screening	Treatment Period		Follow-up	
Visit	1	2	3	4	5
Postoperative day	-1	0a	0b	2	3
Medical history	x				
Physical Examination	x				
Vital signs		x	x	x	x
Concomitant therapy	x	x	x	x	x
In-/Exclusion Criteria	x				
Subject information and informed consent	x				
Pregnancy test	x				
Randomization		x			
Study medication (sevoflurane or propofol)			x		
1° variable: CTC level		x	x	x	x
2° variable A		x	x	x	x
2° variable B*			x		
2° variable C					
Perioperative data	x	x	x	x	x
Safety variables: AE			x	x	x

Visit 1: 24h before surgery

Visit 2 (0a): before induction of anesthesia

Visit 3 (0b): end of surgery, before extubation

Visit 4: 48h after surgery

Visit 5: 72h postoperative, before hospital discharge

Primary variable: assessment of circulating tumor cells in peripheral blood

Secondary variable A: assessment of natural killer (NK) cells (number and activity)

Secondary variable B: extracapsular tumor spread in axillary nodes

* Data will be collected after completion of the study

Perioperative data: demographics and confounding factors

TABLE OF CONTENTS

1.	LIST OF ABBREVIATIONS AND DEFINITIONS OF TERMS	8

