5.2.4 Safety variables

Any adverse event (AE) or serious adverse event (SAE) as described below.

Table 4. Demographics and perioperative data to be collected
Patient data
Age
ASA class
Concomitant therapy
Surgery type
Last menstruation date
TNM stage: size T1-T4; pathological node status N0, N1-3, N>3
Tumor type
Histological tumor grade (grade 1-3)
Receptors (E+/P+; E+/P-; E-/P+; E-/P-; HER2+)
Ki67>35%
Extracapsular tumor spreading
Peroperative data
Anesthesia duration (min)
Mean expiratory fraction in group sevoflurane (Exp%)
Total amount of propofol in group propofol (mg)
Mean BIS value
Total amount of fentanyl (mg)
Mean core temperature (°C)
Administration of b-blockers or COX-inhibitors (yes/no)
Administration of PONV prophylaxis (yes/no)
Blood transfusion (number of units)
Postoperative data
Total amount of morphin in PACU (mg)
Total amount of morphin on the ward (mg)
Administration of b-blockers or COX-inhibitors (yes/no)
Administration of PONV prophylaxis (yes/no)
Blood transfusion (number of units)

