6.4 Study procedures (fig.1)

6.4.1 Visit 1 (preoperative day)

- Standard pre-anesthesia visit: medical history, physical examination, demographics (as listed in Table 1)

- Check for eligibility according to the inclusion and exclusion criteria
- Information of patient and written informed consent
- Pregnancy test: if not pregnant, the patient will qualify for the study
- Concomitant therapy* will be administered
- Potential confounders will be documented

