8.4 Prior and Concomitant Therapy

Patients being on any systemic immunosuppressive therapy (glucocorticoids, cytostatics, antibodies, drugs acting on immunophilins, interferon, TNF bindings proteins, mycophenolate), as well as patients taking chronically opioids, planned for pre-operative chemo- or radiotherapy, or undergoing surgery with concomitant

regional anesthesia (epidural catheter, paravertebral blockade, wound infiltration with local anesthetics) will not be included, as these factors are known to interfere with the immune system.^{84,88,89}

Of note is that patients undergoing *intraoperative* radiotherapy with Intrabeam immediately after removal of the tumor are included. This is a new localized intraoperative “standard of care” therapy in breast cancer.

Long-term medications, such as beta-blockers or COX-inhibitors, as well as perioperative blood transfusion or postoperative opioids, have also been suggested to affect the immune system.^{84,87} However, because the benefits of these treatments outweigh their presumable detrimental effect on the immunity, and because strict avoidance of opioids in the postoperative phase would lead to increased pain and distress, these treatments will not be interrupted nor avoided. Opioids will be administered following a strict protocol mentioned previously (8.4.2.1). Adjustment for residual confounders will be performed at the analytical level.

All concomitant and/or rescue treatment(s) have to be recorded in the eCRF, except for perioperative standard medication such as prophylactic antibiotics or heparin.

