12.3.2 Secondary Analyses

Since most reports refer to CTC levels as a binary outcome (i.e. positive *versus* negative endpoint using a cut-off value of ≥ 5 CTC/7.5ml blood), data transformation from a continuous into a binary variable will be performed using the same cut-off value as described previously. This new data set will be analyzed using a logistic regression mixed model with random effects matrix.

Provided our sample size is large enough, adequate randomization is likely to reduce imbalance in baseline characteristics between groups. However, further exploratory analyses will be performed whenever there is a need to control for residual confounding.

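### Section 5.2.3 lists hypothermia and blood transfusion for controlling residual confounders, but both are recorded only after randomisation and do not fit the baseline-imbalance purpose in 12.3.2

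*Protocol*

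**What the plan says.** - **Protocol 5.2.3** provides for "exploratory analyses whenever there is a need to control for residual confounders, the following variables will be collected: hypothermia, blood transfusion", then COX inhibitors, beta-blockers, glucocorticoids and the date of last menstruation.
- **Protocol 6.1** places randomisation on the day of surgery, "once the patient will be installed for induction of anesthesia". Section 6.4.2 and the study schedule put it at visit 2, before induction.
- **Table 4** (printed under 5.2.4) has mean core temperature only in its peroperative block. Units transfused appear only in the peroperative and postoperative blocks.
- **Protocol 12.3.2** says that "adequate randomization is likely to reduce imbalance in baseline characteristics between groups" and continues that "further exploratory analyses will be performed whenever there is a need to control for residual confounding".
- **Protocol 8.4** discusses long-term beta-blockers and COX inhibitors, perioperative transfusion and postoperative opioids, explains why they are not withheld, and ends: "Adjustment for residual confounders will be performed at the analytical level".
- **Protocol 12.3.1** defines the primary linear mixed model by time and anesthesia regimen. It names none of the variables above.

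**The concern.** A confounder of a randomised comparison has to be in place before allocation. If temperature or transfusion differs between the arms afterwards, the difference is either chance or an effect of the regimen. If it is an effect, adjustment removes whatever part of the treatment effect runs through the variable. Where an unmeasured cause drives both the variable and the CTC count, adjustment can also create a difference that does not exist. Section 5.2.3 therefore names two variables that cannot do the job it gives them, and that 12.3.2, with its reference to baseline characteristics, does not call for.

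Section 8.4 adds an ambiguity. It promises adjustment directly after naming two factors that arise after allocation, and does not repeat that such analyses are exploratory and done only when needed. An analyst who follows 5.2.3 and 8.4 literally could report an adjusted treatment effect that does not answer the question in 12.3.2.

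**Working it through.** **Step 1. When each variable arises, relative to randomisation at visit 2**

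| Variable | Where the protocol records it | Status |
|---|---|---|
| Core temperature (hypothermia) | Table 4, peroperative only | After allocation |
| Blood transfusion | Table 4, peroperative and postoperative only | After allocation |
| Opioid totals (8.4; not in the 5.2.3 list) | Table 4, peroperative and postoperative | After allocation |
| Beta-blockers, COX inhibitors | Named lines per- and postoperatively; long-term use available from concomitant therapy at visit 1 | Long-term use is baseline; use during or after surgery is not |
| Date of last menstruation | Table 4, patient data | Baseline |

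So the list mixes legitimate baseline covariates with two variables that are not.

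**Step 2. The plan's own design figure**

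Inputs from 12.5: effect 0.3, within-subject correlation 0.4, power 80%, two-sided alpha 5%, dropout 10%. The protocol states neither the number of visits nor the correlation structure used. Three post-baseline visits with equal correlation are assumed here because they come closest.

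- Variance of a patient's mean: (1 + 2 × 0.4)/3 = 0.6.
- n per arm = 2 × ((1.960 + 0.842)/0.3)² × 0.6 = 174.42 × 0.6 = 104.65.
- Divided by 0.9: 116.3, against 116 stated. Rounding up to 105 first gives 117.

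With 104 per arm after dropout (116 × 0.9 = 104.4), the unadjusted SE is √(2 × 0.6/104) = 0.107, and power at 0.30 is 79.8%.

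**Step 3. What adjustment for a post-allocation variable would do**

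Let A be the regimen's shift of the variable in SD units, and r its within-arm correlation with a patient's mean CTC. Both are assumptions; the protocol gives no value for either.

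- Within-arm slope: B = r × √0.6.
- Bias relative to the total effect: A × B.
- Adjusted SE: √(2 × 0.6 × (1 − r²)/104 × (1 + A²/4)).

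| A | r | B | Bias | Share of 0.30 | Adjusted estimate | Rejection if there is no true effect and r comes from a common cause |
|---|---|---|---|---|---|---|
| 0 | 0.2 | 0.155 | 0 | 0% | 0.300 | 5.0% |
| 0.1 | 0.1 | 0.077 | 0.008 | 3% | 0.292 | 5.1% |
| 0.2 | 0.2 | 0.155 | 0.031 | 10% | 0.269 | 6.0% |
| 0.3 | 0.3 | 0.232 | 0.070 | 23% | 0.230 | 10.3% |

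A simulation with 6,000 replicates agrees: estimates 0.299, 0.290, 0.268 and 0.230; rejection 5.2%, 5.1%, 5.5% and 10.1%. If core temperature has an SD of 0.3 to 0.5 °C (assumed), A = 0.3 is a shift of 0.09 to 0.15 °C.

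**Step 4. ASA class (separate from the defect)**

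If the stratification factor explains a share R² of the variance and is left out of the model, the actual alpha is about 2 × (1 − Φ(1.96/√(1 − R²))). This gives 4.8%, 4.4% and 3.9% for assumed R² of 2%, 5% and 10%: slightly conservative, with no bias.

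**The case against.** The strongest reply is that no defined analysis is affected. The primary model is fixed without these variables. Sections 5.2.3 and 12.3.2 call the adjusted analyses exploratory, and 5.2.3 says only that the variables are collected, not that each enters a treatment-effect model. Covariate lists for exploratory models are commonly left to the SAP. This stands as a limit on weight. It does not remove the point, because the protocol is not silent: it names particular variables for a particular purpose, and two of them cannot serve it.

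Four stronger readings are tempting and are not supported.

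- *The primary result is biased.* Section 12.3.1 gives no basis for this.
- *Section 8.4 sets a competing, mandatory rule.* Its sentence closes a passage on why some treatments are not stopped, and can be read as shorthand for 12.3.2. The missing condition is an ambiguity to align, not a firm contradiction.
- *The regimen is known to change temperature or transfusion.* The protocol says nothing on this.
- *The schedule legend is a further error.* Its gloss "Perioperative data: demographics and confounding factors" covers genuine baseline items too and adds little.

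It could also be said that pre-randomisation values exist. Section 6.4.1 states "Potential confounders will be documented" at visit 1, and vital signs are taken at visit 2 before induction. But 6.4.1 names neither variable, the content of the vital signs is not given, and Table 4 holds temperature and transfusion only from surgery onwards.

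**Conclusion.** The point holds and is minor. Hypothermia and blood transfusion, as the protocol collects them, arise after allocation. They cannot confound the randomised comparison and do not fit the baseline purpose in 12.3.2. That conclusion rests on the text alone.

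The size cannot be taken from the documents. If the regimen leaves these variables unchanged, the bias is zero. On the assumed grid it reaches 0.070, or 23% of the planned effect, only at the upper corner; the smallest non-zero case gives 3%. These figures depend on the assumed A and r and on the three-visit, equal-correlation reading of the sample size. They concern exploratory models only and do not justify a higher rating. The primary test, the sample size and the power are unaffected.

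**What to change.** State one rule in the same terms in three places.

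1. **12.3.2:** exploratory adjustment addresses baseline imbalance and uses only variables fixed before randomisation, for example age, date of last menstruation, and long-term beta-blocker or COX-inhibitor use taken from concomitant therapy at visit 1.
2. **8.4:** replace the closing promise of adjustment with a statement that adjusted treatment-effect analyses are exploratory and follow 12.3.2.
3. **5.2.3:** state that core temperature, transfusion, opioid totals and drugs given during or after surgery are reported by arm only.

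The cost is wording only. The baseline items named are already collected (Table 4; concomitant therapy at visit 1), and no clinical procedure changes.

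Separately, and not needed to repair this defect, add ASA class as a fixed effect in the primary mixed model, since 8.2 and 12.1 stratify the randomisation by it. With classes I to III this costs two degrees of freedom. It removes the slight conservatism that arises if ASA class is prognostic.
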